Dispensing/collection of trial drug	X	X	X	X			X ⁽¹⁴⁾	X

Figure 1: Schedule of Assessment

Visit Number	Visit 1 ⁽¹⁾	Visit 2 ⁽¹⁾	Visit 3	Visit 4	Visit 5	Telephone contact	Visit 6	Visit 7
Visit Name	Screening/ Placebo Run In	Eligibility assessment/ Randomization (start 10 mg litoxetine or Placebo BID)	1 week Post Randomization First dose escalation (start 20 mg or Placebo BID)	2 weeks Post Randomization Second dose escalation (start 30 mg or Placebo BID)	3 weeks Post Randomization		8 weeks post Randomization Final Treatment Visit⁽⁴⁾ (ET Visit)	13 weeks post Randomization Post-Treatment Safety F/U⁽³⁾ (End of Study Visit)
Study Day ⁽²⁾	Day 0	Day 14	Day 21	Day 28	Day 35	Day 42	Day 70	Day 105
Patient bladder diary review/collection ⁽¹²⁾	X	X					X	
Recording of AEs		X	X	X	X		X	X

Abbreviations: AEs = adverse events; BMI = body mass index; ECG = electrocardiogram; ET = early termination; PVR = postvoid residual urine volume; UTI = urinary tract infection

(1) Eligible subjects will undergo a 2-week Screening Placebo Run-In Period with 7 days bladder daily diary symptom collection. Subjects who continue to be eligible after the Screening Placebo Run-In Period will be randomised (Treatment Period).

(2) Visit window \pm 2 days

(3) AEs must be followed for a minimum of 30 days and until complete resolution or stabilization of the event, or as deemed appropriate by the Investigator on consultation with the Sponsor medical responsible.

(4) If a subject is withdrawn prematurely from the trial, all procedures indicated for the Week 8 (Visit 6) visit must be performed. The Investigator should use every effort to encourage the subject to taper study medication for 1 week and to return for the Safety Follow-up Visit (Visit 7).

(5) Serum pregnancy tests will be performed prior to entry into the trial (Visit 1), the ET Visit (Visit 6; if the subject is discontinuing the study) and at the End of Study Visit (Visit 7) for all female subjects of childbearing potential. Only those female subjects with a negative pregnancy test at Visit 1 will receive trial medication.

(6) Urine (dipstick) pregnancy tests will be performed at Visits 2, 3, 4, 5, and 6 (if it is not the ET Visit) for all female subjects of childbearing potential. Only those female subjects with a negative pregnancy test will receive trial medication.

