6.1 Handling of Missing Data

Missing Data for the Safety Analysis

Partial dates for medications will be imputed. In case of incomplete date, if day and month are missing the first of January is imputed, if only the day is missing the first of the month will be imputed. Completely missing dates will not be imputed.

No other imputation methods are used for missing values in safety variables.

Missing Data for the Efficacy Analysis

The cases where the total number of incontinence episodes is missing will be addressed prior to unblinding with the following multiple imputation process:

1. The imputation method will be applied to the total number of incontinence episodes missing at Visit 6 only.
2. The imputation method will be applied to the number of incontinence episodes only, it will not be applied to the number of pads or to the number of nocturia episodes.
3. The number of imputations will be based on the percentage of missing data.
4. The seed will be set to 1.
5. The imputation process will be applied to the ITT population.

The method of Predictive Mean Matching is proposed for the imputation process. The method imputes the total number of incontinence episodes for each subject with missing value at visit 6. This method does not make an assumption about the distribution of the variables, thereby minimising the risk of assuming normality when not applicable.

With this method a predictive value is computed via a regression model using a set of observed values from cases deemed to be similar to the missing case based on a set of covariates. This methodology is consistent with an assumption of Missing at Random.

For all analyses where the imputation method is used, analyses without imputation will also be performed as sensitivity analyses.

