All AEs (excluding SAEs) will be listed, and their time to onset, frequency, severity, and relationship to the trial drug will be tabulated by treatment. Non-TEAEs will be summarised separately from TEAEs.

A subgroup analysis of TEAEs will be presented. Subjects will be divided according to age (under 65, over 65). The SOCs and PTs will be used for tabulation. The number of TEAEs and the number and the percentage of patients with at least one TEAE will be presented by SOC and PT for each treatment group and according to the patient's age.

An additional analysis will explore the TEAEs that lead to study drug reduction. Results will be presented as listings as well as with means of descriptive statistics.

Withdrawals

Premature withdrawals from the trial will be displayed and summarised by primary reason and treatment.

Physical examination

Abnormal physical examination findings will be summarised. For each physical examination a shift table presenting the number and the percentage of patients in each bivariate category (baseline versus Week 8 (Visit 6)) with regards to investigator's interpretation (Normal, Abnormal NCS, Abnormal CS, Not done) will be provided by treatment group.

The other results of targeted physical examination will be only listed.

Concomitant Medications

Concomitant medications will be presented in summary tables and listings. They will be classified according to whether they were taken before the trial (and ongoing into the trial), or started during the trial period. A medication will be defined as concomitant if taken after the date of informed consent.

The following information will be reported for each concomitant medication: generic name, route of administration, start date, stop date, frequency, dosage, and indication.

Prior Medications

Prior medications will be presented in summary tables and listings. Medications will be classified as prior medications if taken before the date of informed consent.

Vital signs

Vital signs will be summarised by treatment group at each visit (Baseline, Visit 3, Visit 4, Visit 5, Visit 6) by means of descriptive statistics and listed by subject.

Parameters collected include:

1. Heart Rate (bpm)
2. Body Temperature (Degree Centigrade)

An additional analysis will be performed also on radial heart rate. The actual change from baseline to each visit (Visit 3, Visit 4, Visit 5, Visit 6) in radial heart rate will be computed.

Past and Concomitant Diseases

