Categorical analysis will be conducted based on predetermined thresholds (Visit 2, Visit 3, Visit 4, Visit 5, Visit 6):

- Number of subjects with $450 < QT \leq 480$ ms, $480 \text{ ms} < QT \leq 500$ ms and $QT > 500$ ms
- Number of subjects with $450 < QTc \leq 480$ ms, $480 \text{ ms} < QTc \leq 500$ ms and $QTc > 500$ ms

- Number of subjects with increase in QT from baseline >30 ms and <= 60 ms, as well as >60 ms
- Number of subjects with increase in average QTc from baseline >30 ms and <= 60 ms, as well as >60 ms

Tabulation of the results will follow Appendix 1, Guide for the analysis and review of QT and QTc Interval data, Health Canada, 2010.

Psychiatric monitoring

Answers of the questionnaires for psychiatric monitoring will be listed.

In particular, answers for the following questionnaires will be reported:

1. Columbia-Suicide Severity Rating Scale (C-SSRS)
2. Beck Depression Inventory-II (BDI-II)
3. Beck Anxiety Inventory (BAI)
4. Pittsburgh Sleep Quality Index (PSQI)

For the Columbia-Suicide Severity Rating Scale (C-SSRS), summary tables will be used to present the results at visit 1, visit 2, visit 3, visit 4, visit 5, telephone contact at day 42, visit 6 and visit 7. Patients will be classified into 3 categories of subjects with suicidal behaviour, suicidal ideation and suicidal ideation or behaviour according to the Columbia Scoring and Data Analysis Guide (see Appendix 2). Subcategories will also be included. A subject has a suicidal ideation if she/he reports “yes” answer at any time during treatment to any one of the five suicidal ideation questions (Categories 1-5) on the C-SSRS; a suicidal behaviour if there is a “yes” answer to any one of the five suicidal behaviour questions (Categories 6-10); a suicidal ideation or behaviour is the subject has either suicidal ideation or behaviour.

The Suicidal Ideation Score corresponds to the ‘Most severe Ideation’ score reported in the eCRF and it will be presented as listings. A missing suicidal ideation score means no ideation is present. A shift table will be provided to demonstrate changes in C-SSRS categories from Baseline to Visit 6.

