$$\Delta = \exp\left(\log\left(\frac{\%UIE_{Litoxetine}}{\%UIE_{Placebo}}\right)\right) = \frac{\%UIE_{Litoxetine}}{\%UIE_{Placebo}}$$

$\%UIE_i$ is the ratio of the total number of urinary incontinence episodes in a week at endpoint (Visit 6) ($UIE_{i,end}$) to the total number of urinary incontinence episodes in a week at baseline ($UIE_{i,base}$) for arm i , with i equal to Litoxetine or Placebo.

An ANCOVA will be performed to compare δ to 0; the test will provide an appropriate p-value with a significance level alpha equal to 0.05. This p-value will be computing the probability of observing a difference among arms.

Numbers of incontinence episodes equal to 0 (not missing) will be imputed as 0.4 to allow for the log transformation.

2. Absolute change from end of the Screening Placebo Run-In Period to Week 8 in the number of incontinence episodes/24 hours (daily average)

The analysis planned is an analysis of covariance model (ANCOVA). Absolute change in the total number of incontinence episodes/24 hours is the response variable. The factor variables will be dose and centre. The covariate will be end of the Screening Placebo Run-In Period episodes of incontinence.

Number of incontinence episodes/24 hours will be computed as Total Number of incontinence episodes recorded during the 7-day period and entered in the eCRF divided by 7, as defined in Section 5.4.

The hypothesis test being conducted is as follows:

$$H_0: \Delta UIE_{Litoxetine} - \Delta UIE_{Placebo} = 0$$
$$H_1: \Delta UIE_{Litoxetine} - \Delta UIE_{Placebo} \neq 0$$

Where ΔUIE_i is the absolute change, for subjects in arm i , in the number of incontinence episodes/24 hours as defined above from baseline ($UIE_{i,base}$) to the final measurement ($UIE_{i,end}$):

$$\Delta UIE_i = UIE_{i,end} - UIE_{i,base}.$$

Where i goes from 1 to 2 and it represents the 2 arms: Litoxetine and Placebo.

3. Proportion of subjects who become continent at Week 8

A subject is defined as continent if s/he has no incontinence episodes at Visit 6 (Week 8). Frequencies will be used to describe the proportion of subjects who are continent at Week 8. The proportion will be computed on the total number of subjects for each arm at baseline. The category Missing will be included in the analysis, to consider subjects who do not attend the visit or who have missing values for that visit.

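### The C-SSRS missing-score rule does not separate a blank after five negative answers from an assessment that was not done, and the C-SSRS tables state no not-done category or denominator

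*SAP*

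**What the plan says.** SAP 6.8 takes the Suicidal Ideation Score from a single eCRF field, the most severe ideation "score reported in the eCRF and it will be presented as listings". It then adds: "A missing suicidal ideation score means no ideation is present". No condition is attached. The next sentence reads: "A shift table will be provided to demonstrate changes in C-SSRS categories from Baseline to Visit 6".

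Earlier in the same text, the tabulated categories are defined differently. A subject has ideation if there is a positive "answer at any time during treatment to any one of the five suicidal ideation questions (Categories 1-5) on the C-SSRS", and behaviour is defined in the same way on questions 6 to 10. The summaries cover eight contacts: Visits 1 to 7 and the Day 42 telephone call.

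SAP 6.1 allows imputation of partial medication dates and then says: "No other imputation methods are used for missing values in safety variables".

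For subjects who leave early, footnote 4 to the schedule of assessments (SAP Section 3, Figure 1) says: "If a subject is withdrawn prematurely from the trial, all procedures indicated for the Week 8 (Visit 6) visit must be performed". The Visit 6 column of that schedule includes the C-SSRS.

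**The concern.** A blank score can arise in two ways. The C-SSRS may have been completed with no ideation item endorsed, so that there was no severity to record. Or it may not have been done at all. In the first case no ideation is the correct reading. In the second, the rule supplies a value, and always the reassuring one.

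Safety is the primary objective, the drug is a serotonin reuptake inhibitor, and the C-SSRS is the study's instrument for suicide monitoring. A reader of the listings and tables needs to know whether the absence of ideation was observed or assumed. If assessments are missed more often in one arm, treating them as negative would also distort the comparison between arms.

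**Working it through.** No figure in the documents depends on this rule, so there is nothing to reproduce. The check sets the texts side by side and then gives a sense of scale under stated assumptions.

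**1. The rule against the general missing-data rule.** SAP 6.1 rules out imputing missing safety values. SAP 6.8 gives every missing ideation score a meaning. The two agree if the blank follows five negative answers, because nothing is then missing. They disagree if the C-SSRS was not done.

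**2. Where an assessment can be missing.**
- Protocol 8.3 lists failure to return among the withdrawal reasons. Such a subject may have no early-termination assessment.
- The Day 42 call is the only scheduled contact between Day 35 and Day 70. A later early-termination visit does not fill in a missed call.
- Any subject, withdrawn or not, can miss one of the eight contacts.

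**3. The C-SSRS tables against the SAP's other tables.**

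| Analysis | Provision for subjects not assessed |
|---|---|
| Physical examination shift table (6.8) | Not-done category: "Normal, Abnormal NCS, Abnormal CS, Not done) will be provided by treatment group" |
| ECG shift table (6.8) | Same not-done category |
| Continence at Week 8 (6.9) | "The category Missing will be included in the analysis, to consider subjects who do not attend the visit" |
| C-SSRS summary and shift tables (6.8) | None stated; no denominator stated |

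SAP 6.3 and 6.7 assign safety analyses to the Safety Population, but that fixes the analysis set and not the number assessed at each contact. The three named C-SSRS categories (behaviour, ideation, either) are all positive findings. A shift table therefore needs a further cell for subjects with neither, and the SAP does not say whether unassessed subjects belong in it.

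**4. Ceiling from dropout.** SAP 3.1 plans 78 randomised, 30% dropout and 60 evaluable.
- 0.30 × 78 = 23.4, about 23 subjects.
- 78 − 60 = 18 subjects, and 18/78 = 23%.

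The two statements do not agree, so both are carried as a range. Either is an upper bound on subjects with no Visit 6 C-SSRS through dropout, because withdrawn subjects are due one.

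**5. Scale if the rule were carried into a Visit 6 table.** Assumptions: all 52 litoxetine subjects (78 × 2/3) are in the table, no dropout has an early-termination C-SSRS, and all unassessed subjects count as no ideation. The case counts are invented for illustration, and the SAP plans no interval for these tables.

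Recorded rate = rate among those assessed × (assessed / 52). With zero cases, the exact upper 95% limit is 1 − 0.025^(1/n).

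| Dropout | Assessed | Factor | Upper limit, 0 cases, n assessed | Upper limit, 0 of 52 |
|---|---|---|---|---|
| 10% (assumed) | 47 | 0.90 | 7.5% | 6.8% |
| 23% | 40 | 0.77 | 8.8% | 6.8% |
| 30% | 36 | 0.69 | 9.7% | 6.8% |

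With three cases at 30% dropout, 3/36 = 8.3% (exact 95% CI 1.8 to 22.5) would appear as 3/52 = 5.8% (1.2 to 15.9).

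**6. Unequal dropout.** The documents give no rate by arm. Assume a rate of 8% among those assessed in both arms, with 35% dropout on litoxetine (34 of 52 assessed) and 20% on placebo (21 of 26 assessed). The recorded rates become 8% × 34/52 = 5.2% and 8% × 21/26 = 6.5%: an apparent difference where none exists.

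**The case against.** The sentence is attached to a listed severity field. The natural reading is that this field is blank when no ideation item was endorsed, so that the sentence explains a conditional field and imputes nothing. The summary categories use the yes/no answers, so any recorded positive answer still counts. The questionnaire answers are listed too, so a careful reader could tell five negative answers from an empty form. Withdrawn subjects are due a C-SSRS at early termination and are asked back for follow-up, where it is repeated. The primary endpoint list in SAP 2.3 concerns adverse events; C-SSRS scoring is not in it, and the rule changes no adverse event count or interval in 6.7. The SAP also defers to a C-SSRS scoring guide (Appendix 2) that was not available here and might settle denominators.

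All of this stands, and it limits the point. It does not remove it. The benign meaning is plausible, but the SAP does not state it, and a programmer following the sentence would treat both kinds of blank alike. Early-termination assessments do not cover a missed Day 42 call or a subject who never returns.

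A reader might infer more: that skipped assessments and dropouts are tabulated as free of ideation, about 23 of 78 subjects. The documents do not say so. They do not say that the score feeds the tables, or that an entry is created for a visit that never took place.

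**Conclusion.** The point holds as a defect in a stated rule, together with a gap in the table specification. Followed literally, the rule lists a C-SSRS that was not done as no ideation. In those cases it is in tension with SAP 6.1; it is not a contradiction where the form was completed. How unassessed subjects are handled in the summary and shift tables is unspecified.

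The number affected is unknown. Dropout caps the Visit 6 assessments lost by that route at about 18 to 23 of 78, and the true number should be lower if early-termination visits take place. Missed calls and single missed visits are outside that cap. The factors of 0.69 to 0.90 apply only if the rule is carried into the tables with no early-termination assessments. Any imbalance between arms is hypothetical. The point is modest in size, concerns reporting only, and is worth correcting because the instrument monitors suicidality and the correction is cheap.

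**What to change.** Replace the sentence in SAP 6.8 with a conditional rule. A blank ideation score is read as no ideation only when the C-SSRS was completed at that contact and all five ideation answers are no; otherwise the entry is shown as not assessed.

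In the visit summaries and the Baseline-to-Visit 6 shift table, add a not-assessed category, use the number assessed as the denominator, and report the number not assessed by arm and contact, including the Day 42 call.

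The cost is one SAP sentence, one programming condition and an extra row or column in the tables. Denominators will be smaller, and any intervals calculated on them slightly wider. If the benign reading was intended, the rule change alters no listed value for a completed form and only makes that reading explicit.

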Suicidal Adverse Events and Adverse Events suggestive of abuse potential will be summarised by treatment group. The SOCs and PTs will be used for tabulation. The number of AEs and the number and the percentage of patients with at least one AE will be presented by SOC and PT for each treatment group. Within each SOC and PT, the highest severity grade attained will be reported, for AEs with divergent severities.

Adverse events will be described with point estimates and Clopper Pearson 95% confidence intervals.

4. Laboratory parameters (Haematology, chemistry, and urinalysis)

Abnormal laboratory values will be listed and their incidence, severity, and relationship to the trial drug will be tabulated by treatment. Change from baseline will be summarised by treatment. Individual changes (shift tables) and individual clinically significant abnormalities will also be presented.

While total white blood cell (WBC) count will be expressed in absolute values, differential count will be expressed as both absolute count and percentage of WBCs.

Haematology and chemistry parameters will be summarised by treatment at each visit (visit 2 and visit 6) by means of descriptive statistics. At each visit, mean of the change from baseline will be calculated by treatment group. For Electrolytes only, values at visit 3, visit 4 and visit 5 will also be summarised. In special cases, other parameters may be collected at visit 3, visit 4 and visit 5. In that case the results will be included in the summary statistics.

Shift tables presenting the number and the percentage of patients in each bivariate category (Baseline (Visit 2) versus Endpoint (Visit 6)) with regards to normal range (Low, Normal, High) will be provided for all laboratory parameters (Haematology and chemistry) by treatment group.

For liver enzymes (ALT, AST) and total bilirubin additional analysis will be performed with values expressed in ULN (upper limit of normal) in incidence tables ($>3\times$ ULN, $>5\times$ ULN, and $>10\times$ ULN for aminotransferase activities, and for total bilirubin $>2\times$ ULN).

The pregnancy test and the urinalysis will be listed only. In particular, the serum pregnancy test is performed at visit 1, visit 6 and visit 7, while the urine (dipstick) pregnancy test is performed at visit 2, visit 3, visit 4, visit 5 and visit 6. Urinalysis is performed at visit 1 and 2.

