The medical history should include demographic information, urinary and incontinence history (with date of onset), past treatment(s) for incontinence, current co morbidities, relevant past illnesses, surgical

procedures performed within the prior 6 months, all current medications (including those taken within 30 days prior to Screening), and smoking history (including current usage, if applicable).

Past and concomitant diseases will be coded using MedDRA dictionary (version 20.1) and frequency distributions and percentages will be summarised by treatment group for the safety population by SOC and PT.

Counts will be given for both SOC and PT by subject. Subjects experiencing more than one past disease (or concomitant disease) event within a given SOC category will be counted only once within that SOC. Similarly, subjects experiencing more than one past disease (or concomitant disease) event fitting a given PT will be counted only once for that PT.

Summary tabulations for the Safety Population, including the number and percentage of subjects with past and concomitant diseases by SOC and PT, and further categorised by treatment arm will be added.

12-Lead ECG

Actual values and also change from baseline in ECG readings at Visit 2 (baseline), Visit 3, Visit 4, Visit 5, Visit 6 will be summarised by descriptive statistics.

ECG parameters of interest include:

1. Ventricular rate
2. QT interval
3. Corrected QT interval
4. PR interval
5. RR interval
6. QRS duration.

All three measurements for each parameter will be reported. A shift table presenting the number and the percentage of patients in each bivariate category (Baseline to Endpoint) with regards to investigator's interpretation (Normal, Abnormal NCS, Abnormal CS, Not done) will be provided by treatment group.

QT will be corrected for HR using the following formulas:

- Fridericia's correction ($QTc=QT/RR^{0.33}$),
- Bazett's correction ($QTc=QT/RR^{0.5}$)
- Framingham correction ($QTc=QT+0.154(1-RR)$)

Change in QT and QTc for each correction method, will be analysed by central tendency and as categorical analyses. The mean of the QT and HR (obtained in triplicate) will be used.

Central tendency analysis will include:

- Change from baseline (V2) at all time points.
- The change from baseline to Visit 6 in active treatment group will be compared to placebo with a two-sided t-test. The level of significance alpha will be set equal to 5%.
- Results will be reported by 95% CI

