The BDI-II is a widely used 21-item self-report inventory measuring the severity of depression in adolescents and adults. BDI-II items are rated on a 4-point scale ranging from 0 to 3 based on the severity of each item. The maximum total score is 63. The total score derived in the eCRF will be summarized. Patients will also be classified according to the following rules: total scores of 0 to 13 indicates minimal depression, 14 to 19 indicates mild depression, 20 to 28 indicates moderate depression, and 29 to 63 indicates severe depression. A summary table will be used to describe the results at visit 1, visit 2, visit 3, visit 4, visit 5, visit 6 and visit 7. See Appendix 3 for more details on this questionnaire. A shift table will be provided to demonstrate changes in BDI-II categories from Baseline (Visit 2) to end of study (Visit 6).

The Beck Anxiety Inventory (BAI) is a widely used 21-item self-reported inventory used to assess anxiety levels in adults and adolescents. Summary tables will be used to present the total score at visit 1, visit 2, visit 3, visit 4, visit 5, visit 6 and visit 7. The total score will be computed summing up the score to each question.

The total score ranges from 0–63. The following categories for the interpretation of scores will be used: 0–7, minimal; 8–15, mild; 16–25, moderate; and 26–63, severe anxiety. A shift table will be provided to demonstrate changes in BAI categories from Baseline (Visit 2) to end of study (Visit 6).

See Appendix 4 for more details on this questionnaire.

The Pittsburgh Sleep Quality Index (PSQI) is an effective instrument used to measure the quality and patterns of sleep in adults. It differentiates “poor” from “good” sleep quality by measuring seven areas (components): subjective sleep quality (question 6), sleep latency (question 2 and 5A), sleep duration

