(question 4), habitual sleep efficiency (questions 1, 3, 4), sleep disturbances (question 5B to 5J inclusive), use of sleeping medications (question 7), and daytime dysfunction over the last month (questions 8 and 9). In scoring the PSQI, seven component scores are derived, each scored 0 (no difficulty) to 3 (severe difficulty). The component scores are summed to produce a global score (range 0 to 21). Higher scores indicate worse sleep quality. The global score reported in the eCRF will be summarized at visit 1, visit 2, visit 3, visit 4, visit 5, visit 6 and visit 7. A global sum greater than “5” indicates a “poor” sleeper, therefore patients will be classified according to the global score into “good” or “poor” sleepers, a summary table will be provided to describe those results. A shift table will be provided to demonstrate changes in PSQI categories from Baseline to end of study (Visit 6). See Appendix 5 for more details on this questionnaire.

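### The shift tables stop at Visit 6: add a once-per-subject shift from baseline to worst on-treatment category

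*SAP*

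**What the plan says.** SAP 6.8 plans for the C-SSRS: "A shift table will be provided to demonstrate changes in C-SSRS categories from Baseline to Visit 6". For the BDI-II: "A shift table will be provided to demonstrate changes in BDI-II categories from Baseline (Visit 2) to end of study (Visit 6". The BAI and PSQI sentences have the same form. SAP 5.5 sets baseline for safety variables at Visit 2.

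For haematology and chemistry, SAP 6.7 item 4 tabulates each "bivariate category (Baseline (Visit 2) versus Endpoint (Visit 6)) with regards to normal range (Low, Normal, High". For the investigator's ECG interpretation, SAP 6.8 plans: "A shift table presenting the number and the percentage of patients in each bivariate category (Baseline to Endpoint". Endpoint means Visit 6 wherever the SAP defines it, and this ECG table includes a Not done category.

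The schedule of assessments (SAP Figure 1; Protocol Appendix 2) also places the four scales, the ECG and electrolytes at Visits 3, 4 and 5. It adds a C-SSRS-only telephone contact on Day 42. Note 4 to the schedule requires a subject withdrawn early to have all Visit 6 procedures.

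For the C-SSRS, SAP 6.8 also classifies a subject as having ideation on a yes "answer at any time during treatment to any one of the five suicidal ideation questions". It then reads a missing ideation score as absence of ideation.

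**The concern.** Safety and tolerability are the primary objective, and the adverse event endpoints cover the whole study. Visits 3 to 5 span the titration and the first week at the top dose level. SAP section 3 allows a dose reduction for a subject who does not tolerate that level. A category change in this window can therefore appear and resolve before Visit 6, and the shift table then shows the subject as unchanged.

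A shift table is the one display that ties a subject's category to that subject's own baseline category and counts the subject once. If it uses only the last on-treatment assessment, it cannot answer a basic question for a safety trial: how many subjects had a worse category than at baseline at any point on treatment?

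**Working it through.** The plan states no figure on this point, so there is nothing to reproduce. The check sets the schedule against the planned displays.

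| Measure | On-treatment assessments | Shift table uses | Other displays covering Visits 3-5 | Once-per-subject worst category against baseline? |
|---|---|---|---|---|
| Electrolytes | Visits 3, 4, 5, 6 (4) | Visit 6 | Descriptive summaries; incidence of abnormal values | No |
| Other laboratory tests | Visit 6 (1); Visits 3-5 only in special cases | Visit 6 | Special-case values join the summaries | Little to miss |
| ECG interpretation | Visits 3, 4, 5, 6 (4) | Visit 6 | No table stated | No |
| QT/QTc | Visits 3, 4, 5, 6 (4) | Not applicable | Threshold counts and increases from own baseline, per visit | Per visit only; no on-treatment maximum stated |
| C-SSRS | Visits 3, 4, 5, Day 42, Visit 6 (5) | Visit 6 | Summaries at each visit and Day 42 | Any-time classification defined; shift uses Visit 6 |
| BDI-II | Visits 3, 4, 5, 6 (4) | Visit 6 | Results summarised by visit | No |
| BAI | Visits 3, 4, 5, 6 (4) | Visit 6 | Total score by visit; by-visit categories not stated | No |
| PSQI | Visits 3, 4, 5, 6 (4) | Visit 6 | Global score by visit; good/poor sleeper summary | No |

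**Share of assessments used.** The shift tables use 1 of 4 on-treatment assessments, or 1 of 5 for the C-SSRS.

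**Early leavers: an upper bound only.**
- The plan randomises about 78 subjects 2:1, so 78 × 2/3 = 52 go to litoxetine.
- At the stated 30% dropout, 0.30 × 52 = 15.6, about 16 litoxetine subjects.
- The stated 60 evaluable implies 78 − 60 = 18 leavers, of whom 18 × 2/3 = 12 are on litoxetine.
- The two planning figures do not agree, so both are shown.
- Either number would lack Visit 6 data only if every leaver also missed the required early-termination assessments. The likely number is lower and cannot be derived from the documents.

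**Illustration with assumed rates.** The documents give no rate of transient category change. Suppose the chance of a worse category is p at each of four visits. Visit 6 alone then finds p. If visits were independent, any visit would find 1 − (1 − p)^4:
- p = 2%: 1 − 0.98^4 = 7.8%
- p = 3%: 1 − 0.97^4 = 11.5%
- p = 5%: 1 − 0.95^4 = 18.5%

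If the same subjects were abnormal at every visit, any visit would also find p and there would be no gap. The true figure lies between p and the value shown. Visits a week apart in the same person are not independent, so it falls short of the upper end.

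**Missing C-SSRS.** Reading a blank ideation score as no ideation is reasonable when the interview took place and every answer was no. The SAP does not separate that case from an assessment that was not done. A subject without a Visit 6 C-SSRS could therefore be tabulated as free of ideation.

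**The case against.** The strongest reply is that a reader might infer that transient safety changes vanish from the report, and the documents do not support that.

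- ECG values and changes from baseline are summarised at Visits 3 to 6. QT and QTc increases above 30 and 60 ms are counted against each subject's own baseline at each visit.
- Abnormal laboratory values are listed and their incidence tabulated, with no limit to Visit 6.
- Clinically relevant laboratory changes are recorded as adverse events (Protocol 6.1.2.2; SAP 5.3) and so enter the primary analysis. Psychiatric and suicidal events have their own tables with exact confidence intervals.
- All questionnaire answers are listed, and all four scales are summarised by visit.

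A reader might also see a contradiction between the any-time C-SSRS definition and the Visit 6 shift. These are two displays with different purposes and can stand together.

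Nor can one say that the tables cover only subjects who tolerated treatment to Week 8. Visit 6 doubles as the early-termination visit, and withdrawn subjects are to have all its procedures.

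The point is also narrower than laboratory shift tables in general. Only electrolytes are scheduled at Visits 3 to 5, and Day 42 concerns the C-SSRS alone. PSQI readings a week apart overlap, because the instrument includes a component over the last month. The SAP says QT tabulation follows a cited guide that is not reproduced, so it may bring in a maximum that the SAP text does not state.

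All of this stands. It limits the point to one missing kind of summary. By-visit means and totals, per-visit counts and listings do not show how many subjects moved to a worse category at any time on treatment.

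**Conclusion.** The gap is real but modest. The shift tables for laboratory values, ECG interpretation, C-SSRS, BDI-II, BAI and PSQI compare baseline with Visit 6 only. No planned display counts each subject once by worst on-treatment category against baseline for electrolytes, ECG interpretation, BDI-II, BAI or PSQI. QT/QTc categories are stated per visit, so subjects with any exceedance cannot be counted from those tables.

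This is a reporting improvement worth making because safety is the primary objective. It is not an error that hides safety signals, and it does not touch the primary adverse event analysis.

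Its numerical effect cannot be estimated from the documents. The 16 of 52 is an upper bound, and the any-visit percentages are an illustration on assumed rates. The conclusion needs neither. It rests on the schedule, on the wording of the shift tables, and on reading Endpoint in the ECG table as Visit 6.

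**What to change.** Keep each Visit 6 shift table and make these additions in SAP 6.7 and 6.8:

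- **Worst-case shift.** Add baseline to worst on-treatment category for laboratory values (in practice mainly electrolytes), ECG interpretation, C-SSRS, BDI-II, BAI and PSQI. Use Visits 3 to 6, including early-termination and unscheduled values, plus Day 42 for the C-SSRS only. For electrolytes, show lowest and highest separately, since abnormality can go either way.
- **Denominator.** Use all Safety Population subjects with at least one post-baseline value of that measure, and print the number.
- **QT/QTc.** Add an on-treatment maximum row to the threshold and increase-from-baseline tables.
- **Missing records.** State that early-termination values count. Show a subject with no Visit 6 C-SSRS assessment as missing, not as having no ideation.

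The cost is SAP wording and a little programming, with no new data. Worst-case rates will be slightly higher than Visit 6 rates in both arms, and they depend on how many assessments a subject has. The Visit 6 column should therefore stay alongside. If unblinding has already occurred, label the additions post hoc.
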